6.4 Sample Size and Power

We expect to prospectively identify approximately 139 patients and assuming 90% of identified patients will be discharge eligible and 85% will consent, the anticipated study population will be 118 patients and their caregivers. Approximately 40% will be managed as outpatients, so we expect 47 outpatients and 71 inpatients. The power calculation was conducted under the framework of a multivariate general linear hypothesis for general linear models, using the Wilks Lambda test with a significance level of 0.05 (35, 36). Assuming a standard deviation (SD) of 20 for the PedsQL™ total score, if there is no correlation we will have 80% power to detect a large effect size of 0.75 that is a 15.0 point difference in the mean change scores between the two groups. If the correlation is as high as 0.8 we will have 80% power to detect a small effect size of 0.34, that is a 6.8 point difference in the mean change scores between the two groups.

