Treatment for pediatric acute myeloid leukemia (AML) or myelodysplastic syndrome (MDS) involves intensive chemotherapy regimens that result in periods of profound neutropenia leaving patients susceptible to severe infectious complications. Infectious complications are the leading cause of treatment related mortality among AML and MDS patients, but there are little clinical data to inform whether management of neutropenia post AML chemotherapy should occur in an outpatient or inpatient setting. Further, no studies have been conducted that assess the impact of neutropenia management strategy on the quality of life of pediatric patients with AML/MDS and their caregivers.

Objectives:

The primary objective of this study is to compare patient and caregiver quality of life and other patient-centered outcomes (PCO) for inpatient versus outpatient management of neutropenia in children with AML or MDS receiving standard intensive AML frontline chemotherapy.

Study Design:

This is a prospective observational cohort study.

Setting/Participants:

[figure not shown]
Participants will be patients less than 19 years of age at their initial AML or MDS diagnosis (and their caregivers) receiving or having received frontline AML chemotherapy from fifteen participating pediatric hospitals across the United States (US). Due to the nature of the survey collected data, only dyads who are English/Spanish literate will be eligible. We expect to identify 139 patient-caregiver dyads, of which we anticipate that approximately 118 will consent to participate over the study period to compare patient- and caregiver-identified outcomes of neutropenia management in the outpatient and inpatient settings.

Study Interventions and Measures:

There is no study intervention. Main outcomes include scores on health-related quality of life surveys, as well as additional patient- and caregiver- identified outcomes.

TABLE 1: SCHEDULE OF STUDY PROCEDURES

Study Phase	Screening	Study Visits	
Visit Number		1	2
Informed Consent/Assent	X		
Review inclusion/exclusion criteria	X		
Baseline PedsQL™		X	
Demographic survey		X	
Demographic survey II		X	
Follow-up PedsQL™			X
PCO survey			X
Financial toxicity survey		X	X

FIGURE 1: STUDY DIAGRAM

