3.3.2 Total Number of Study Sites/Total Number of Subjects Projected

Surveys will be administered at the following fifteen US investigative sites: Children's Hospital of Philadelphia (*Philadelphia, PA*), Children's Healthcare of Atlanta (*Atlanta, GA*), C.S. Mott Children's Hospital (*Ann Arbor, MI*), Ann & Robert H Lurie Children's Hospital of Chicago (*Chicago, IL*), Arkansas Children's Hospital (*Little Rock, AR*), Children's Medical Center of Dallas (*Dallas, TX*), Texas Children's Hospital (*Houston, TX*), Primary Children's Medical Center (*Salt Lake City, UT*), Children's Hospital of Michigan (*Detroit, MI*), Lucile Packard Children's Hospital Stanford (*Palo Alto, CA*), St. Jude Children's Research Hospital (*Memphis, TN*), Seattle Children's Hospital (*Seattle, WA*), Children's Hospital Colorado (*Denver*), Nemours/A.I. duPont Hospital for Children, and DFCI/Boston Children's Hospital (*Boston, MA*). These sites were chosen based on geographic location, their substantial AML/MDS patient volume, and the variation in primary strategy of neutropenia management.

We expect approximately 278 subjects across all sites to be enrolled and approximately 236 subjects to be evaluable (118 patients and 118 caregivers).

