3.4 Study Population

The study population will include all AML and MDS patients who are receiving a planned frontline chemotherapy course at any of the fifteen pediatric institutions across the US starting June 1, 2016. Patients discharged within 3 days after chemotherapy completion will be categorized as 'early discharge' to outpatient management during neutropenia. Patients remaining in the hospital more than 3 days after chemotherapy completion will be categorized as inpatient management.

Caregivers of these patients will also be included.

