4.5.1 Early Termination Study Visit

Child-caregiver dyads who withdraw from the study during or prior to completion of the follow-up surveys will only be compensated a portion of the \$50 for the visits they do complete.

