We will utilize linear mixed effect models to test the association between neutropenia management strategy and the PedsQL™ total score. Specifically, the two repeated measures of the PedsQL™ total score will be the outcome and regressed on time, group (outpatient versus inpatient) and interaction between time and group will be the fixed effects, and a subject level random effect will be included to account for the potential correlations between the repeated measures. Such mixed models are more powerful than ANCOVA or analysis of change scores, and they benefit from the added power arising from any correlation of repeated measures over time. A significant group by time interaction will suggest that the change of PedsQL™ is different between the two groups. Adjustment for differences in covariates across neutropenia management groups will be accomplished through the propensity score outlined above, and by controlling for confounding of any remaining unbalanced potential confounders. Secondary analyses will be performed for the cancer and fatigue modules as well as for the physical and psychosocial subscales of the PedsQL™.

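### The enrolment figures in section 6.4 do not multiply out (139 × 90% × 85% is 106, not 118), and section 3.3.2 gives 139 and 118 a different meaning from the abstract and 6.4

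*Combined protocol and SAP*

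**What the plan says.** Three places give the expected numbers.

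- Section 6.4, Sample Size and Power: "We expect to prospectively identify approximately 139 patients", and then, "assuming 90% of identified patients will be discharge eligible and 85% will consent, the anticipated study population will be 118 patients and their caregivers". About 40% are expected to be managed as outpatients, giving 47 outpatients and 71 inpatients. With an SD of 20, the section claims 80% power for a 15.0-point difference in mean change at correlation 0, and for 6.8 points at correlation 0.8.
- Abstract, Setting/Participants: "We expect to identify 139 patient-caregiver dyads, of which we anticipate that approximately 118 will consent to participate". There is no discharge-eligibility step.
- Section 3.3.2: "We expect approximately 278 subjects across all sites to be enrolled and approximately 236 subjects to be evaluable (118 patients and 118 caregivers").

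Three further sections bear on how to read these figures. Section 3.4 defines the population broadly: "The study population will include all AML and MDS patients who are receiving a planned frontline chemotherapy course". Sections 3.4.1.1 and 3.4.1.2 do not list discharge eligibility among the criteria. Section 4.5.1 provides for "Child-caregiver dyads who withdraw from the study during or prior to completion of the follow-up surveys".

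**The concern.** Section 6.4 names two successive reductions, but its total reflects only one. The 90% clause could be a real filter that was left out of the sum, a leftover that should have been deleted, or a step already taken in reaching 139. These readings lead to different expected sample sizes.

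Separately, the same 15% loss does two jobs. In the abstract and 6.4 it is refusal of consent, before enrolment. In 3.3.2 it is non-evaluability, after enrolment. One loss cannot be both. If 118 is the number consenting, 6.4 allows nothing for dyads that never reach Visit 2, and the primary test (the group-by-time interaction) needs both visits.

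At stake is the study's only sample-size justification. A reader cannot tell the enrolment target, or whether the stated power refers to dyads who consent or to dyads with usable data.

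**Working it through.** **Inputs.** From 6.4: 139 identified, 90% discharge eligible, 85% consenting, 118 in the study, 40% outpatient (47/71), two-sided alpha 0.05, SD 20, correlation r of 0 or 0.8. From 3.3.2: 278 subjects enrolled, 236 evaluable.

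**1. The funnel.**
- Both rates: 139 × 0.90 × 0.85 = 106.3. This is about 12 patients, or 10%, below 118.
- Consent only: 139 × 0.85 = 118.15, which matches 118.
- Discharge eligibility only: 139 × 0.90 = 125.1.
- Working back with both rates: 118 / (0.90 × 0.85) = 154.2 identified.

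No use of both rates on 139 gives 118.

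**2. Section 3.3.2.** 278 / 2 = 139 dyads enrolled, 236 / 2 = 118 dyads evaluable, and 236 / 278 = 0.849. This is the same 85% ratio, placed after enrolment.

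**3. The plan's power, reproduced.** A one-degree-of-freedom group-by-time test on two visits is equivalent to a two-sample t-test on change scores, with SD of change = 20 × √(2(1 − r)). That is 28.28 at r = 0 and 12.65 at r = 0.8. The noncentrality is the difference divided by [SD of change × √(1/n₁ + 1/n₂)].
- 47/71, 15.0 points, r = 0: 15.0 / (28.28 × 0.1880) = 2.820; power 79.9%.
- 47/71, 6.8 points, r = 0.8: 6.8 / (12.65 × 0.1880) = 2.859; power 80.9%.

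The stated 80% is confirmed at 118.

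**4. If the 90% is a filter on 139.** 0.4 × 106 = 42.4, so about 42 outpatients and 64 inpatients.

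| | 47/71 | 42/64 |
|---|---|---|
| Power, 15.0 points, r = 0 | 79.9% | 75.4% |
| Power, 6.8 points, r = 0.8 | 80.9% | 76.5% |
| Detectable with 80% power, r = 0 | 15.0 | 15.9 |
| Detectable with 80% power, r = 0.8 | 6.7 | 7.1 |

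**5. If 118 is the number consenting.** The documents give no rate of Visit 2 loss, so 5%, 10% and 15% are assumptions, taken as equal in the two groups. The planned model, in which "a subject level random effect will be included to account for the potential correlations between the repeated measures", can keep dyads with a baseline only. With a fraction m missing Visit 2, the variance of a group's mean change is 20²/n × [(1 − r²)/(1 − m) + (1 − r)²]. For m = 0 this reduces to 20²/n × 2(1 − r). The powers below use a normal approximation, so compare them with its own no-loss row and not with step 3.

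| Visit 2 missing | 15.0 points, r = 0 | 6.8 points, r = 0.8 |
|---|---|---|
| 0% | 80.5% | 81.6% |
| 5% | 79.5% | 79.8% |
| 10% | 78.4% | 77.8% |
| 15% | 77.1% | 75.7% |

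At 15% missing, leaving baseline-only dyads out multiplies the noncentrality by √0.85. It becomes 2.600 and 2.636, with power 73.9% and 75.0%. Keeping those dyads therefore recovers only part of the loss.

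**The case against.** The strongest reply is that the documents lean away from the harmful reading. The abstract goes from 139 to 118 by consent alone, section 3.4 takes in every patient on a planned frontline course, and no eligibility criterion concerns discharge. The figure 118 appears in all three places, and the group sizes and power follow from it. A stray clause is therefore a likely explanation, and then the power is unaffected. Even in the worst case the detectable differences move by 0.9 and 0.3 points, far less than the plan's own range of 6.8 to 15.0 across correlations, and the counts are described as approximate. On labels, the abstract and 6.4 agree with each other. Only 3.3.2 departs, and its 139 is inferred from 278.

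Most of this stands, and it limits the size of the problem. It does not repair the text. Section 6.4 applies its 90% explicitly to the identified patients ("assuming 90% of identified patients will be discharge eligible") and calls 139 the number identified. A 10% gap is too wide for rounding. That a leftover clause is likely is an inference that only the sponsor can confirm. Section 3.3.2 might be read as already allowing for loss to follow-up, but then the consent statements in the abstract and 6.4 are wrong.

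**Conclusion.** The derivation in 6.4 is wrong as written, and 3.3.2 conflicts with the abstract and 6.4 on what 139 and 118 count. It should be corrected, though the effect is modest and conditional.

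- If the 90% is a real filter on 139, power falls by about 4.5 and 4.4 points from the reproduced values (79.9% to 75.4%, and 80.9% to 76.5%). Against the nominal 80%, the shortfalls are 4.6 and 3.5 points.
- If it is not a filter, or 139 is already the discharge-eligible count, 118 and the stated power stand.
- If 118 is the number consenting, Visit 2 loss lowers power further, by an amount the documents do not allow one to fix. Under the assumed losses of 5% to 15%, it is 79.5% to 77.1% at r = 0 and 79.8% to 75.7% at r = 0.8.

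These figures rest on the plan's SD of 20, its two correlations and its 40% outpatient share.

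**What to change.** State which reading applies, and use the same stages (identified, discharge-eligible if relevant, consenting, evaluable) in the abstract, 3.3.2 and 6.4:

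- (a) 139 identified, 125 discharge-eligible, 106 consenting, with groups restated as 42 and 64 and detectable differences as 15.9 and 7.1 points; or
- (b) about 154 identified, 139 discharge-eligible, 118 consenting; or
- (c) the 90% clause deleted because discharge eligibility does not limit enrolment, leaving 139 identified and 118 consenting.

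Also state whether 118 is the number consenting or the number evaluable. If consenting, correct 3.3.2, give the expected number with both visits, and base the power statement on that number. If evaluable, as in 3.3.2, reword the consent statements in the abstract and 6.4.

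The cost is text edits in three places. Under (b) or (c) the group sizes and power stay as they are unless a Visit 2 loss is added. Under (a) the detectable differences become slightly less favourable. None of these adds to the number enrolled beyond 118. Option (b) does require about 15 more patients to be identified than the text states, unless 139 was always the discharge-eligible count.

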Visit 2 will occur within the period after absolute neutrophil count recovery and ideally prior to the start of the subsequent course of chemotherapy, but no later than the last day of chemotherapy in that next treatment course. For the small number of patients who will begin the next course of chemotherapy before count recovery, Visit 2 will occur within the period from one day prior to the start of chemotherapy in that next treatment course and no later than the last day of chemotherapy in that course. This visit will include:

- 3 follow-up health-related quality of life (HRQOL) PedsQL™ surveys (core, cancer, and fatigue)
- 1 PCO survey
- 1 Financial toxicity survey

All surveys will be administered via paper or a smart device and will last a total of 15-30 minutes per respondent. In the case that the child is 5 years of age or older, the PedsQL child self-report and parent proxy-report scales will be administered to the child and caregiver, respectively. If the child is between 5 and 8 years of age, Study Personnel will read the survey questions to the patient. There is an illustrated response aid for these young patients. These age-specific PedsQL instruments have been previously validated. The child will indicate their answer as 'Not at all', 'Sometimes', or 'A lot' by pointing to a smiling, middle, or frowning face, respectively. If the child is under 5 years of age, only the parent-proxy version will be administered. Caregivers will also be asked to complete the PCO

survey at follow-up. The PCO survey assesses dimensions such as parental stress and anxiety, patient's sleep behaviors, impact on siblings, and hospital discharge teaching practices. In addition, caregivers will be asked to complete the financial toxicity survey again at follow-up. The caregiver completing the follow-up assessments must be the same caregiver who completed the baseline assessments. We will provide a \$50 gift card to each child-parent dyad upon completion of the PCO survey, financial toxicity survey, and follow-up quality of life surveys. If the child and caregiver do not complete both visits, they will only be compensated a portion of the \$50 for the visits they do complete.

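### Section 6.4 counts 118 consenting dyads as complete two-visit pairs, while Section 3.3.2 calls the same 118 evaluable; the 80% power leaves no room for loss before Visit 2

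*Combined protocol and SAP*

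**What the plan says.** Section 6.4 starts from about 139 identified patients, names a discharge-eligibility rate and a consent rate, and arrives at its sample size: "85% will consent, the anticipated study population will be 118 patients and their caregivers". All 118 are then divided into 47 outpatients and 71 inpatients. Power is for the difference between groups in mean change over two visits. "Assuming a standard deviation (SD) of 20 for the PedsQL™ total score", the plan claims "80% power to detect a large effect size of 0.75 that is a 15.0 point difference in the mean change scores" if the two visits are uncorrelated, and "80% power to detect a small effect size of 0.34, that is a 6.8 point difference" if the correlation is 0.8. No step after consent appears in the calculation.

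The abstract agrees that the 118 are the dyads who consent, out of 139 identified. Section 3.3.2 gives the same numbers another meaning. It expects "approximately 278 subjects across all sites to be enrolled and approximately 236 subjects to be evaluable", that is, 139 dyads enrolled and 118 evaluable.

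Elsewhere the protocol makes room for incomplete dyads without estimating how many there will be. Section 4.5 allows withdrawal at any time. Section 4.5.1 sets part payment for "dyads who withdraw from the study during or prior to completion of the follow-up surveys", and Sections 4.4 and 8.6.1 do the same for dyads who miss a visit. Section 4.4 also rules that "The caregiver completing the follow-up assessments must be the same caregiver who completed the baseline assessments". The primary analysis in Section 6.3.1 is a linear mixed model on both visits, tested through the group-by-time interaction.

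**The concern.** A difference in mean change is informed mainly by dyads seen at both visits. If 118 is the number who consent, a sample size with no allowance for loss assumes that practically nobody withdraws, becomes too ill, or misses the Visit 2 window, in children on intensive chemotherapy. The 80% would then overstate what the study can do on its primary endpoint. If 118 is the number evaluable, the power statement is sound but Section 6.4 and the abstract describe the wrong quantity, and the recruitment count no longer fits. A reader cannot tell from the documents which applies.

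**Working it through.** **Inputs.** From Section 6.4: SD 20 at each visit; correlation ρ = 0 or 0.8; significance level 0.05; differences 15.0 and 6.8 points; groups of 47 and 71. With two groups and one change contrast, the Wilks Lambda test is the two-sided t test on change scores.

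**Reproducing the plan.**
- SD of change = 20 × √(2(1 − ρ)) = 28.28 at ρ = 0 and 12.65 at ρ = 0.8.
- Standard error = SD of change × √(1/47 + 1/71) = SD of change × 0.188 = 5.319 and 2.379.
- Noncentrality = 15.0/5.319 = 2.82 and 6.8/2.379 = 2.86, on 47 + 71 − 2 = 116 degrees of freedom.
- Power (noncentral t) = **79.9%** and **80.9%**. The differences with exactly 80% power are 15.03 and 6.72 points.

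The printed figures are therefore right for 118 complete pairs. At a 40/60 split, 80% power needs 119 pairs at ρ = 0 and 116 at ρ = 0.8, so there is essentially no reserve.

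**What 118 stands for.** 139 × 0.85 = 118.2, and 236/278 = 0.849. The 85% that Section 6.4 calls consent and the enrolled-to-evaluable ratio in Section 3.3.2 are the same 139-to-118 step under two names. If 139 dyads really were enrolled after 85% consent, about 139/0.85 = 164 would have to be approached, whereas Section 6.4 and the abstract identify only 139.

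**Effect of Visit 2 loss from 118 consenters.** The documents give no rate, so 5% to 20% is an assumed range, equal in both groups. For complete pairs the same t test is used with the reduced group sizes. For the mixed model, Visit 1-only records are kept and data are taken as missing at random. With n dyads at Visit 1 and m at both visits, the variance of mean change in a group is 400 × [(1 − ρ²)/m + (1 − ρ)²/n]. Example at 15% loss, ρ = 0: 400 × (1/40 + 1/47 + 1/60 + 1/71) = 30.8, so the standard error is 5.55, against 5.77 on complete pairs.

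| Loss | Pairs | Power, complete pairs (ρ 0 / 0.8) | Power, mixed model (ρ 0 / 0.8) | 80%-power difference, complete pairs (ρ 0 / 0.8) |
|---|---|---|---|---|
| 0% | 47 + 71 | 79.9% / 80.9% | 79.9% / 80.9% | 15.0 / 6.7 |
| 5% | 45 + 67 | 77.9% / 79.0% | 78.8% / 79.1% | 15.4 / 6.9 |
| 10% | 42 + 64 | 75.4% / 76.5% | 77.5% / 76.9% | 15.9 / 7.1 |
| 15% | 40 + 60 | 73.0% / 74.1% | 76.3% / 74.8% | 16.3 / 7.3 |
| 20% | 38 + 57 | 70.8% / 71.9% | 75.1% / 72.8% | 16.8 / 7.5 |

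The mixed-model column uses whole-number pairs and the complete-pair degrees of freedom. Unrounded group sizes with 116 degrees of freedom change it by at most 0.2 points.

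**The case against.** The strongest defence is Section 3.3.2. If 139 dyads enrol and 118 are evaluable, a 15% loss has already been deducted and the power rests on the right number. That reading is possible, but it contradicts Section 6.4 and the abstract, where 118 is the number who consent. It turns the point into a conflict to be resolved rather than removing it.

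Three further arguments have some force:
- The planned mixed model can use a Visit 1-only record. At ρ = 0 this recovers roughly half the lost power; at ρ = 0.8 it recovers little.
- Loss may be low. Section 3.3.1 puts participation at about 30 to 40 days, and the Visit 2 window in Section 4.4 extends to the last day of the next chemotherapy course. At 5% loss the power stays within about 2 points of 80%.
- Section 6.4 already spans 6.8 to 15.0 points, and even 20% loss moves those ends only to 7.5 and 16.8.

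Some stronger readings are tempting but unsupported:
- A reader might take the 15% in Section 3.3.2 as a further loss on 118 and arrive at about 100 pairs as the planned number. That uses one 15% twice (139 × 0.85 × 0.85 = 100.4). The 15% row in the table is only one point of the assumed range.
- A reader might infer that a follow-up by a different caregiver is void. Section 4.4 requires the same caregiver but states no rule for discarding data, and child self-report does not depend on which caregiver responds.
- The payment and withdrawal text provides for incomplete dyads. It does not forecast them.
- Nor does the claim need literally every dyad: 116 pairs suffice at ρ = 0.8.

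**Conclusion.** The point holds in a limited form. The power arithmetic is correct for 118 complete pairs. What is wrong is that Section 6.4 and the abstract describe those 118 as consenters, with no allowance for a missing Visit 2, while Section 3.3.2 describes them as evaluable. On the Section 6.4 description, the stated 80% is not delivered under ordinary loss. The shortfall on complete pairs is about 2 points of power at 5% loss and about 9 at 20%. With the mixed model it is 1.1 (ρ = 0) or 1.8 (ρ = 0.8) points at 5%, and 4.8 or 8.1 at 20%. This is modest, but it falls on the power claim for the primary endpoint.

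These sizes rest on an assumed loss rate, equal loss in both groups, 118 consenters as the base and, for the mixed model, data missing at random. Propensity-score adjustment and clustering by hospital are not modelled. The 90% discharge-eligibility factor that Section 6.4 names but does not apply (139 × 0.90 × 0.85 = 106) is a separate matter and is not included in the table.

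**What to change.** 1. Reconcile the abstract, Section 3.3.2 and Section 6.4 on whether 118 is the number of consenting or of evaluable dyads, and use one term throughout.
2. In Section 6.4, state an expected Visit 2 completion rate as an explicit assumption with its basis, and base the power statement on the dyads expected to have both visits. Do not carry the 15% from Section 3.3.2 over as an additional loss on 118.
3. If 118 means consenters, restate the 80%-power differences from the last column of the table for the chosen rate, for example 15.9 and 7.1 points at 10% loss. If the mixed model is to be credited for Visit 1-only records, say so and name the missing-at-random assumption.
4. If 118 means evaluable dyads, keep the printed differences, and correct the description of 118 and the recruitment count in Section 6.4 and the abstract.

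Under step 3 the cost is rewording and slightly larger stated detectable differences, with no extra patients. Keeping 118 complete pairs instead would take 118/(1 − loss) consenting dyads: 125, 132, 139 or 148 at 5%, 10%, 15% or 20% loss.
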